5.4 Preparation and Administration of Study Drug

Study drug will be prepared in the research pharmacy.

Pretreatment: Fifteen minutes prior to the first infusion, 100 mg methylprednisolone will be administered via IV along with 1000 mg acetaminophen and 50 mg diphenhydramine given by mouth. Fifteen minutes prior to all subsequent infusions, only 1000 mg acetaminophen and 50 mg diphenhydramine will be administered by mouth.

First Infusion and those part of OLE being retreated due to relapse (16 mg/Kg): IV infusion in 1000 mL 0.9% NaCl via 0.2 or 0.22 micron in-line filter, beginning at 50 mL/hr. Increase by 50 mL/hr every 60 minutes, as tolerated, to a maximum rate of 200 mL/hr. Vital signs will be taken every 15 minutes for first hour, then every hour until end of infusion, and then again after IV flush.

Second Infusion (16mg/Kg): IV infusion in 500 mL 0.9% NaCl via 0.2 or 0.22 micron in-line filter, beginning at 50 mL/hr. Increase by 50 mL/hr every 60 minutes, as tolerated, to maximum rate of 200 mL/hr. If the first infusion was not well tolerated (infusion-related reaction > Grade 1), then instructions for the first infusion should be used. Vital signs will be taken every 15 minutes for first hour, then every hour until end of infusion, and then again after IV flush.

Subsequent Infusions(16 mg/Kg): IV infusion in 500 mL 0.9% NaCl via 0.2 or 0.22 micron in-line filter, beginning at 100 mL/hr. Increase by 50 mL/hr every 60 minutes, as tolerated, to maximum rate of 200 mL/hr. If the previous infusion was not well tolerated (infusion-related reaction > Grade 1), then instructions for the second infusion will be used. Vital signs will be taken every 15 minutes for first hour, then every hour until end of infusion, and then again after IV flush.

Infusion related reactions: Diphenhydramine 25 mg IV can be given every 4 hours as needed and may repeat once if symptoms are not relieved within 15 minutes of initial dose. Methylprednisolone 100 mg IV can be given as needed for infusion related reactions.

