Post-infusion: All patients should receive dexamethasone 4 mg by mouth once daily with food for two days beginning the day after daratumumab. In addition, acyclovir 400 mg by mouth twice daily, beginning within one week of starting daratumumab, and continuing for 3 months after the last daratumumab infusion. Beginning the day after their first daratumumab infusion, patients will also start single strength Bactrim once a day (or its equivalent) to prevent opportunistic infections, including pneumocystis pneumonia. Treatment with Bactrim will continue for six months after the last daratumumab infusion.

A worksheet will be created specifically for this study, which would include a dose calculation with a double check by another pharmacist for added safety. The drug will be prepared in the following steps.

1. Prepared in the non-hazardous sterile hood.
2. Drug volume calculated based upon the 16 mg/kg dose.
3. Utilize 0.9% 1000 mL for the first dose, then 0.9% 500 mL for subsequent doses.
4. Remove drug volume from 0.9% IV bag.
5. Infusion rate instructions:

Continuous Infusion: 1st and 2nd doses: Start infusion at 50 mL/hr. Rate may be increased by 50 mL/hour every hour to a maximum rate of 200 mL/hour.

Subsequent doses: Start infusion at 100 mL/hr. Rate may be increased by 50 mL/hour every hour to a maximum rate of 200 mL/hour.

6. Light protect IV bag.

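### Section 5.4 gives two sets of bag volumes and start rates: the numbered steps omit the reaction and OLE conditions, so starting mg/hr differs 2-fold after a reaction and 1- to 4-fold at OLE retreatment

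*Combined protocol and SAP*

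**What the plan says.** Section 5.4 (Preparation and Administration of Study Drug) describes volume and rate twice.

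The infusion instructions come first.
- First infusion and OLE: "First Infusion and those part of OLE being retreated due to relapse (16 mg/Kg): IV infusion in 1000 mL 0.9% NaCl", starting at 50 mL/hr.
- Second infusion: "Second Infusion (16mg/Kg): IV infusion in 500 mL 0.9% NaCl via 0.2 or 0.22 micron in-line filter, beginning at 50 mL/hr". There is an exception: "If the first infusion was not well tolerated (infusion-related reaction > Grade 1), then instructions for the first infusion should be used".
- Later infusions: 500 mL from 100 mL/hr. If the previous infusion caused a reaction above Grade 1, the second-infusion instructions apply instead (500 mL from 50 mL/hr).

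The numbered steps for preparing the drug follow, after mention of a study-specific worksheet.
- Volume: "Utilize 0.9% 1000 mL for the first dose, then 0.9% 500 mL for subsequent doses".
- Rate: 50 mL/hr for the first and second doses, then "Subsequent doses: Start infusion at 100 mL/hr".
- They mention neither a previous reaction nor the OLE.

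Premedication is also tied to a dose position: "Fifteen minutes prior to the first infusion, 100 mg methylprednisolone will be administered via IV". Note 7 to the Test and Monitoring Schedule in section 6 likewise links methylprednisolone to the first infusion, with later use only as needed. Neither place says whether an OLE course has a new first infusion.

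**The concern.** The numbered steps tell staff how the drug is prepared, and they cover rates as well as volumes. The cases in which they can part from the infusion instructions are the ones for which those instructions made special provision: a patient who has just reacted, and a patient starting an OLE course. Two members of staff, each following section 5.4 correctly, could start the same patient at different mg/hr.

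Safety is the primary objective, and section 1.4 names infusion-related reaction as the most common side effect (48%). Section 8.3.3.3 lists infusion reactions of Grade 3 or above as events of special interest. If starting intensity after a reaction or in the OLE depends on which part of section 5.4 was used, reaction counts from those infusions mix two regimens, and the reader of the results cannot separate them.

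**Working it through.** The documents state no mg/hr figure, so there is none to reproduce. The check compares the starting mg/hr under the two parts of section 5.4.

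**Inputs (section 5.4).** The dose D is the same in both parts: "Drug volume calculated based upon the 16 mg/kg dose". Step 4 takes the drug volume out of the saline bag, so I take the final volume as the nominal bag volume in both parts.

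**Formula.** Starting mg/hr = D × start rate (mL/hr) ÷ bag volume (mL).

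- 1000 mL from 50 mL/hr: D × 50/1000 = 0.05 D per hour
- 500 mL from 50 mL/hr: D × 50/500 = 0.10 D per hour
- 500 mL from 100 mL/hr: D × 100/500 = 0.20 D per hour

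For an assumed 70 kg patient, D = 16 × 70 = 1120 mg, which gives 56, 112 and 224 mg/hr. Weight cancels in the ratios.

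**Main study.** With no previous reaction, the two parts agree at every dose. After a reaction above Grade 1:

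| Situation | Infusion instructions | Numbered steps | Ratio | What differs |
|---|---|---|---|---|
| Dose 2 | 1000 mL, 50 mL/hr | 500 mL, 50 mL/hr | 0.10/0.05 = 2 | bag only |
| Dose 3 or later | 500 mL, 50 mL/hr | 500 mL, 100 mL/hr | 0.20/0.10 = 2 | rate only |

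**OLE retreatment (no reaction in that course).** Two things are unstated: whether the numbered steps count doses across the whole study or restart with each course, and whether the OLE clause covers all 12 infusions of a course or only the first.

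- Count runs across the study, bag and rate both from the numbered steps: the first OLE dose is 0.20/0.05 = 4.
- Count runs across the study, bag from the numbered steps but rate from the infusion instructions: 0.10/0.05 = 2.
- Count restarts, clause covers the whole course: 0.05/0.05 = 1 at OLE dose 1, 0.10/0.05 = 2 at dose 2, and 0.20/0.05 = 4 at doses 3 to 12.
- Count restarts, clause covers only the first OLE infusion: 1 throughout, so no conflict.

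**Beyond the start.** Both parts step up by 50 mL/hr each hour to at most 200 mL/hr. At that cap only a bag difference remains: D × 200/500 against D × 200/1000, a ratio of 2. Minimum infusion times are:
- 1000 mL from 50 mL/hr: 50 + 100 + 150 = 300 mL in 3 h, then 700/200 = 3.5 h, total 6.5 h
- 500 mL from 50 mL/hr: 300 mL in 3 h, then 200/200 = 1 h, total 4.0 h
- 500 mL from 100 mL/hr: 100 + 150 = 250 mL in 2 h, then 250/200 = 1.25 h, total 3.25 h

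**Patients affected.** This cannot be computed. The 48% in section 1.4 is not broken down by grade, while the trigger is a reaction above Grade 1. The 9 patients in section 7.2 are expected OLE entrants, and only those who relapse are retreated.

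**The case against.** The best defence is that this is an omission and not a contradiction. Both parts belong to one section, they match for every main-study dose without a previous reaction, and nothing in the numbered steps cancels the exceptions. A careful reader could treat the steps as defaults and the infusion instructions as defaults plus exceptions. The worksheet, which is not in the documents, might carry the conditions. The total dose is unchanged, rate increases are made only as tolerated, and infusion reactions are neither a primary nor a secondary endpoint (sections 3.2 and 3.3).

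Much of this stands and limits the size of the point, but it does not remove it. The numbered steps are worded as complete rules by dose number, and nothing in section 5.4 says that the earlier conditions override them. The pharmacist double check is described for the dose calculation, not for bag or rate.

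Several stronger readings are tempting and are not supported:
- *A 4-fold difference after a reaction.* Under the stated step-back only the bag or only the rate differs, which gives 2. Reaching 4 at dose 3 or later means chaining the step-back from the second-infusion to the first-infusion instructions, which the text does not clearly direct.
- *Pharmacy works from one part, infusion unit from the other.* The documents do not say so. If it were so, the ratios would be 2 at dose 2, 1 at dose 3 or later and, with the first OLE dose counted across the study, 2 there; never 4.
- *The first OLE dose is at least the 17th.* Sections 4.4.1 and 5.5 tolerate some missed infusions. The ratio is unaffected, since the steps treat every dose after the second alike.
- *About 6 of 12 patients, or 9 OLE patients, are affected.* The available figures do not measure the relevant events.
- *Methylprednisolone is contradictory.* Section 5.4 and note 7 agree with each other. What is missing is a definition of first infusion for an OLE course.

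**Conclusion.** The inconsistency is real and is in the current text of section 5.4. If the numbered steps are followed literally, the starting mg/hr after a reaction above Grade 1 is 2 times that of the infusion instructions, through the bag at dose 2 and through the rate at dose 3 or later. At OLE retreatment the ratio ranges from 1 to 4. The value of 4 at the first OLE dose needs doses counted across the whole study and both bag and rate taken from the numbered steps. On one combination of readings the OLE conflict disappears, while the post-reaction conflict remains.

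These ratios assume that the final volume equals the nominal bag volume; they do not depend on weight. How many patients are affected is unknown. Nothing here bears on which volume, rate or premedication rule is right.

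**What to change.** Reconcile the two parts of section 5.4 into one volume and start-rate table, used by both the pharmacy worksheet and the infusion unit. It needs rows for infusion 1, infusion 2, later infusions, the infusion after a reaction above Grade 1, and the first and later infusions of each OLE course. State whether *first dose* and *first infusion* restart with an OLE course, and apply the same definition to the methylprednisolone premedication in section 5.4 and in note 7 of section 6. The sponsor decides which existing instruction governs each row; no interim rule is proposed.

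The cost is a protocol clarification and a matching worksheet, with no added patients or procedures. Bag size and chair time may change for some infusions, depending on what the sponsor confirms.

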5.5 Subject Compliance Monitoring

This drug is administered intravenously in the CRU and we can ensure compliance. If patient misses more than one infusion within the first 8 weeks or more than two infusions in the following 4 months the subject will be withdrawn from the study. We will continue to follow the subject as part of the research study with blood and urine studies and clinic visits to ensure safety.

5.6 Prior and Concomitant Therapy

The patient should be off of all immunosuppressive therapies (cyclophosphamide, MMF, cyclosporine, tacrolimus, azathioprine, ACTH) within three months of enrollment in the study. If patient has received rituximab prior to the study there should be evidence of B-cell reconstitution prior to enrollment (CD 20 count >5). The subject should be off of prednisone or glucocorticoid equivalent in the last 6 weeks prior to enrollment, unless they are being treated with low dose oral prednisone or glucocorticoid for a condition unrelated to PGNMID or C3GN (e.g., asthma, gout) at a daily dose of 10mg or less.

Patients can receive ACE-I or ARB while enrolled in the study but dose adjustment is not allowed unless down titration for safety reasons.

Rescue treatment is not permitted while receiving daratumumab. If patient is failing treatment with evidence of disease progression (> 50% increase in proteinuria and > 30% reduction in GFR based on creatinine clearance) on visit day 77, the subject will be withdrawn from the study and can then receive other immunosuppressive therapy per discretion of the treating physician.

Management of Hepatitis B Virus Reactivation

Primary antiviral prophylaxis is permitted as per local standard of care. Per protocol, HBV DNA testing by PCR is mandatory for subjects at risk for HBV reactivation see Section 6.

For subjects who are diagnosed with HBV reactivation while on treatment, study treatment should be interrupted until the infection is adequately controlled. If the benefits outweigh the risks, study treatment may be resumed with concomitant antiviral prophylaxis as per local standard of care. Consult a liver disease specialist as clinically indicated.

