1.1 Background

Monoclonal gammopathy (MG) are well known to cause kidney damage. The most common example is light chain deposition disease that occurs commonly in the setting of multiple myeloma.¹ Over the last several years, however, there is more recognition that many kidney lesions are associated with low-grade plasma cell dyscrasia or lymphoproliferative disorders.² In fact the term monoclonal gammopathy of renal significance (MGRS) has been introduced to capture kidney lesions associated with monoclonal gammopathy (MG) in the absence of multiple myeloma.³ One of the lesions commonly encountered in patients with MGRS is proliferative glomerulonephritis with monoclonal immunoglobulin deposition (PGNMID) where damage is caused by direct deposition of the monoclonals with associated inflammation.⁴⁻⁶ Another is C3 glomerulopathy (C3 GN) in the setting of MG where the monoclonals result in activation of complement pathway and indirectly result in renal injury.⁷⁻⁹ PGNMID and C3 GN associated with MG are diagnosed based on renal biopsy. Majority of patients present with hematuria and proteinuria and many have a progressive course with loss of renal function over time. Up to 70% of patients with PGNMID may have negative serum electrophoresis with immunofixation, normal serum free light chains and no clone may be identified on bone marrow biopsy.⁶ Treatment of patients with PGNMID and C3GN associated with MG should be directed towards the pathologic clone. There is currently no standardized treatment for these patients and treatments vary based on clinical practice. We currently use combination of cyclophosphamide, bortezomib and dexamethasone in patients with IgG and IgA monoclonals, and rituximab in patients with IgM monoclonals.¹⁰ The current treatments however, have had limited success rate and are associated with significant side effects. There is a desperate need for additional therapeutic options in this population. The high expression of CD38 on plasma cells and low expression on other myeloid cells makes CD38 an appealing target for monoclonal antibody therapy such as daratumumab. Daratumumab has been efficacious in treatment of patients with refractory multiple myeloma and overall is well-tolerated.¹¹ We propose use of daratumumab as first or second line agent in patients with PGNMID and C3GN associated with MG.

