3.3 Secondary Endpoints

Proportion of patients achieving complete or partial remission where the responses are defined as below:

- a) Complete Response at 12 months
 - < 300 mg proteinuria/24 hours
 - No greater than a 15% reduction in GFR as determined by creatinine clearance
- b) Partial Response at 12 months
 - > 50% reduction in 24 hour proteinuria
 - No greater than a 30% reduction in baseline GFR as determined by creatinine clearance
- c) No Response at 12 months
 - \leq 50% reduction, unchanged or increasing proteinuria over baseline levels

- A greater than a 30% reduction in baseline GFR as determined by creatinine clearance
- d) Improvement in hematuria (Categorical: <3 rbc/hpf; 3-10 rbc/hpf; 10 to 50; 50 to 100; >100 rbc/hpf)
- e) Improvement in complement 3 level (increase of 25% from baseline)

4 Subject Selection Enrollment and Withdrawal

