4.2 Exclusion Criteria

- Pregnancy
- Seropositive for human immunodeficiency virus (HIV)
- Seropositive for hepatitis B (defined as a positive test for hepatitis B surface antigen [HBsAg] Subjects with resolved infection (ie, subjects who are HBsAg negative but positive for antibodies to hepatitis B core antigen [anti-HBc] and/or antibodies to hepatitis B surface antigen [anti-HBs]) must be screened using real-time polymerase chain reaction (PCR) measurement of hepatitis B virus (HBV) DNA levels. Those who are PCR positive will be excluded. EXCEPTION: Subjects with serologic findings suggestive of HBV vaccination (anti-HBs positivity as the only serologic marker) AND a known history of prior HBV vaccination, do not need to be tested for HBV DNA by PCR)
- Seropositive for hepatitis C (except in the setting of a sustained virologic response [SVR], defined as aviremia at least 12 weeks after completion of antiviral therapy).
- Multiple myeloma
- Anemia with Hgb $<$ 8.5 g/dL
- Thrombocytopenia with platelet count $<$ 100,000
- Leukopenia with WBC $<$ 3.5
- Any other disease, metabolic dysfunction, physical examination finding, or clinical laboratory finding giving reasonable suspicion of a disease or condition that contraindicates the use of an investigational drug or that may affect the interpretation of the results or render the patient at high risk from treatment complication
- Unable to provide consent
- Patients receiving therapy with oral prednisone or glucocorticoid equivalent in the last 6 weeks. Patients treated with low dose oral prednisone or glucocorticoid are allowed to be included if they are taking the medication for conditions unrelated to PGNMID or C3GN (e.g., asthma, gout) at a daily dose of 10mg or less.
- Patients who had received immunosuppressive therapy with cyclophosphamide, in the last 3 months

- Patients treated with MMF, cyclosporine, tacrolimus or azathioprine are allowed to be included if proteinuria has not improved or is worsening despite these medications and/or kidney function is worsening despite treatment with any of these medications. Once treatment with daratumumab is started, these medications will be discontinued.
- Patients who received rituximab previously with CD20 count of zero at the time of enrollment

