7.2 Statistical Methods

Descriptive Statistics

Univariate descriptive statistics and frequency distributions will be calculated, as appropriate for all variables. Baseline values for demographic, clinical, and outcome variables (primary and secondary) in each response category will be tabulated. Time-to-response will be analyzed descriptively with Kaplan-Meier method.

For the primary endpoint, the number and proportion of patients with treatment-emergent major infections, grade 3 or 4 anemia, leukopenia or thrombocytopenia will be summarized. Changes in Hgb, WBC count and platelet count from baseline (Day 0) will be analyzed through a paired t-test by comparing post-baseline to baseline values. The secondary endpoint of the proportion of patients with complete or partial response will be summarized in a similar manner.

It is expected that 9 patients will enter the OLE. The rate of relapse in addition to the time to relapse from the last dose of daratumumab to initiation of retreatment will be evaluated. Paired t-test will be used to evaluate change in the proteinuria from time of relapse to the end of the study. Rate of CR and PR will be evaluated at the end of the OLE.

Handling of Missing Data

This is a study of only 12 patients and expect that majority of patients will have complete data available.

Primary Hypothesis: Daratumumab is safe and well-tolerated in patients with PGNMID and C3GN associated with monoclonal gammopathy

To test this hypothesis, the incidence of major infection will be examined, specifically the development of pneumonia, severe urinary tract infection/pyelonephritis, sepsis, meningitis will be reported. In addition, anemia, leukopenia, thrombocytopenia will be examined by evaluating changes in Hgb, WBC count and platelet count, respectively. Statistical significance will be assessed using paired t-test comparing 6 months and 1 year value compared to baseline. The

number of patients who had to discontinue drug due to side effect (drop in blood counts, infection) will also be reported.

Secondary Hypothesis: Daratumumab is effective in inducing remission (defined as improvement in proteinuria and eGFR) in patients with PGNMID and C3GN associated with monoclonal gammopathy

A paired t-test will be performed to assess change in proteinuria and renal function at 6 months and 12 months compared to baseline (screening visit).

Interim Analysis

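### No unchanged ACE-I/ARB dose is required before the screening collection used as the proteinuria baseline, so a recent start or increase can bias partial response toward daratumumab

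*Combined protocol and SAP*

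**What the plan says.** On background renin-angiotensin treatment there is one rule, in Section 5.6: "Patients can receive ACE-I or ARB while enrolled in the study but dose adjustment is not allowed unless down titration for safety reasons". The inclusion criteria (4.1) ask for at least 1000 mg of proteinuria over 24 hours and set no condition on how long the ACE-I/ARB dose has been unchanged. The exclusion criteria (4.2) are silent on it too.

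The schedule in Section 6 shows one pre-treatment 24-hour urine protein, at screening. Under the secondary hypothesis in 7.2 Statistical Methods, proteinuria and renal function at 6 and 12 months are "compared to baseline (screening visit", by paired t-test. PR at 12 months (3.3) requires "> 50% reduction in 24 hour proteinuria" plus a limit on GFR loss. All 12 patients receive daratumumab (5.3).

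Other recent treatment is restricted. Section 5.6 says: "The patient should be off of all immunosuppressive therapies (cyclophosphamide, MMF, cyclosporine, tacrolimus, azathioprine, ACTH) within three months of enrollment in the study". Section 4.2 excludes "Patients who had received immunosuppressive therapy with cyclophosphamide, in the last 3 months" and "Patients receiving therapy with oral prednisone or glucocorticoid equivalent in the last 6 weeks", the latter with a low-dose exception, and both sections restrict prior rituximab by CD20 count.

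**The concern.** The protocol bars ACE-I/ARB dose changes on study, which is sensible where proteinuria is the outcome. The same reasoning applies just before the baseline collection, and there the rule does not reach. A patient whose drug was started or raised a week before screening meets every written criterion, with a baseline that may not yet reflect the new dose. Any later fall from that change is counted with the fall from daratumumab, and a single-arm trial cannot separate the two.

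At stake are the PR rate and the paired proteinuria change. Because Section 3.2 follows patients in complete or partial remission into the extension, a misclassified partial responder could also enter the extension analyses.

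**Working it through.** The plan has no figure to reproduce: Section 7.1 states that no power calculation was done, and no effect size, standard deviation or significance level is given. The calculation below only illustrates size.

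**From the documents:** PR needs a fall of more than 50% (3.3); N = 12 with no control (5.3); entry proteinuria is at least 1000 mg/24 h (4.1); complete response (CR) needs less than 300 mg/24 h (3.3).

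**Assumed:** carry-over c of 20%, 30% or 40%, arising wholly after baseline and lasting to month 12; log-normal change in proteinuria with SD of log change s = 0.5 (range 0.3 to 0.7); 4 of 12 patients affected. The GFR condition is ignored, so the counts are on the high side.

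**Step 1, the lowered threshold.** If d is the further fall, PR needs (1 − c)(1 − d) < 0.5, so d > 1 − 0.5/(1 − c).

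- c = 20%: 1 − 0.5/0.8 = 37.5%
- c = 30%: 1 − 0.5/0.7 = 28.6%
- c = 40%: 1 − 0.5/0.6 = 16.7%

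**Step 2, chance of meeting the PR proteinuria criterion with no daratumumab effect.** P = Φ((ln 0.5 − ln(1 − c))/s). With 4 of 12 affected, the expected count is 4P(c) + 8P(0).

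| c | P, s = 0.5 | P, s = 0.3 to 0.7 | Expected of 12, 4 affected, s = 0.5 |
|---|---|---|---|
| 0 | 8.3% | 1.0% to 16.1% | 0.99 |
| 20% | 17.4% | 5.9% to 25.1% | 1.36 |
| 30% | 25.0% | 13.1% to 31.5% | 1.66 |
| 40% | 35.8% | 27.2% to 39.7% | 2.09 |

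The excess over no carry-over is 0.37, 0.67 and 1.10 patients. With 2 affected, the expected count is 1.18 to 1.54; with 6 affected, 1.54 to 2.64.

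**Step 3, one patient.** 1/12 = 8.3 percentage points of the response rate.

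**Step 4, the paired change.** With 4 of 12 affected and no drug effect, the geometric mean ratio to baseline is (1 − c)^(4/12): 0.8^(1/3) = 0.93, 0.7^(1/3) = 0.89, 0.6^(1/3) = 0.84. The apparent mean fall is 7%, 11% or 16%. As an outer bound only, if all 12 were affected, a two-sided 5% paired t-test on the log scale with s = 0.5 would show a significant fall with probability 29%, 62% or 90%, against 2.5% with no carry-over.

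**Step 5, does carry-over reach a response alone?** The assumed 20% to 40% is below the 50% needed for PR. For CR, at the entry minimum, 1000 × 0.6 = 600 mg, twice the 300 mg limit.

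**The case against.** Several points can fairly be made for the plan.

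- *The freeze may already start at baseline.* Section 3.1 establishes baseline values after consent. If enrolment means consent, dose changes are barred from the screening collection onward, and a new start is most naturally barred too. This stands in part, but enrolment is not defined in that way, new starts are not mentioned, and no reading reaches a change made before consent.
- *The size is assumed.* This stands. The documents give neither the effect of an ACE-I/ARB change nor the number of patients likely to have one. Safety down-titration, the one change allowed, would work against a false response.
- *Efficacy is secondary in an unpowered proof-of-concept study.* This also stands and limits the weight of the point. Efficacy is nevertheless a stated hypothesis with its own test.

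A reader might also infer that bortezomib is free of any washout, because Section 1.1 says "We currently use combination of cyclophosphamide, bortezomib and dexamethasone in patients with IgG and IgA monoclonals" while neither 4.2 nor the bracket in 5.6 names it. The documents do not support that. The sentence in 5.6 covers all immunosuppressive therapies, and Sections 1.1 and 1.4 mention bortezomib only alongside cyclophosphamide, which is already held for three months. What remains is unclear wording: the bracket lists six drugs with no sign that they are examples, and 4.2 applies the three-month interval to cyclophosphamide alone. Section 4.2 also admits some patients still taking MMF, cyclosporine, tacrolimus or azathioprine, whereas 5.6 requires them to be off these drugs. The two sections must be reconciled, since they decide on what treatment the baseline is measured.

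**Conclusion.** The gap is real for ACE-I/ARB. As written, the plan allows a start or increase just before the baseline collection, and the bias runs toward daratumumab for PR and for the paired proteinuria test. Under assumed carry-over of 20% to 40%, the further fall needed for PR is 37.5% to 17% instead of 50%. With 4 of 12 patients affected and s = 0.5, that is roughly 0.4 to 1.1 extra apparent proteinuria responders. These figures rest wholly on the stated assumptions.

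Two stronger readings should not be drawn. One is that carry-over alone would be scored as a response: at the assumed sizes it falls short of the PR threshold, and the proteinuria criterion for CR is an absolute level, not a change from baseline. The other is that prior treatment distorts the primary safety endpoint through lowered baseline blood counts: the documents say nothing about such an effect, and 4.2 excludes patients with low hemoglobin, platelets or white cells at entry. The point therefore concerns the secondary efficacy results. It is worth correcting because the correction is specific and cheap.

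**What to change.** 1. In 4.1 and 5.6, require that the baseline 24-hour collection be taken only after the ACE-I/ARB dose has been unchanged for a period that the sponsor sets. State that the existing freeze runs from that collection, and say whether it covers new starts.
2. Record the date of the last ACE-I/ARB change and the dates of prior clone-directed therapy for every patient. In 7.2, add that for any patient already enrolled with a change shortly before baseline, CR/PR and the proteinuria change will be reported with and without that patient.
3. As a wording matter only, reconcile 4.2 with 5.6 so that it is clear which prior immunosuppressive drugs are covered, including whether bortezomib is. Any interval is for the sponsor to set.

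The cost is a few sentences and some added date fields. Some candidates would wait a short time before their baseline collection, which may slow recruitment slightly in a rare disease. Item 2 remains possible after enrolment has begun, provided the dates can be recovered from source records.
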